9. SAFETY EVALUATION

9.1. Demographic and Other Baseline Characteristics

Summaries of age, sex, height, weight, BMI, ethnicity, and race will be presented by treatment group as well as geographic region, comorbidities, duration of symptoms prior to randomization, and actual baseline ordinal score ([Table 54](#) and [Table 55](#)). Ethnicity will be categorized as Hispanic or Latino, or not Hispanic and not Latino. In accordance with NIH reporting policy, subjects may self-designate as belonging to more than one race or may refuse to identify a race, the latter reflected in the CRF as “No” to each racial option.

Individual subject listings will be presented for all demographics and baseline characteristics ([Listing 7](#)).

9.1.1. Prior and Concurrent Medical Conditions

Focused medical history is obtained at the screening visit that includes the following:

- History of chronic medical conditions related to inclusion and exclusion criteria
- Review medications and therapies for this current illness.

Medical history is limited to the following conditions: asthma, autoimmune hepatitis, cancer, cardiac arrhythmia, cardiac valvular disease, chronic kidney disease, chronic liver disease, chronic oxygen requirement, chronic respiratory disease, coagulopathy, congestive heart failure, coronary artery disease, current nicotine consumption, depression or psychotic disorder, diabetes I and II, epilepsy/seizure, hypertension, immune deficiency, obesity, systemic lupus erythematosus, and thyroid disease. History and risk factors for DVT/PE, major surgery in the past month, prolonged immobility, delivery in the past 6 weeks, pre-COVID oxygen use, blood type, and COVID-19 vaccination are also collected. All current illnesses and past pre-existing medical conditions will be MedDRA® coded using MedDRA dictionary version 23.0 or higher. Summaries of subjects’ pre-existing medical conditions will be presented by treatment group ([Table 56](#)).

Individual subject listings will be presented for all medical conditions ([Listing 8](#)).

9.1.2. Prior and Concomitant Medications

Medication history (concomitant medications) includes a review of all current medications and medications taken within 7 days prior to enrollment through approximately Day 15 or early termination (if Day 15), whichever occurs first.

Summaries of medications that were started prior to dosing and continued at the time of dosing or started after dosing while on study will be presented by WHO Drug Level 1 and 2 Codes, actual baseline ordinal score, and treatment group ([Table 57](#)). Summaries of overall use of medications/therapies of interest listed in Section [6.4](#) that were started prior to dosing and continued at the time of dosing or started after dosing while on study as well as use by select study days will also be generated ([Table 58](#) and [Table 59](#)).

Individual subject listings will be presented for all concomitant medications ([Listing 9](#)), corticosteroid use ([Listing 10](#)), and medications of interest ([Listing 11](#)).

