3.3.2. Study Day and Time to Event

Use of "Day 29" or "Day 15" are references to actual study days and represent 28 and 14 days post-randomization, respectively. References to visits such as "Study Visit Day 29" and "Study Visit Day 15" pertain to protocol-defined visits which may occur on any day within the defined visit window and not necessarily on Day 29 and Day 15.

Time-to-event endpoints are based on actual study days, e.g., Day 29 or Day 15. Endpoints that are not specifically defined as a time-to-event are based on Study Visits, irrespective of the study day upon which the visit was conducted. As a result, time-to-event endpoints at Day 15 and Day 29 may not match corresponding Clinical Status Ordinal Scores at Study Visit Day 15 and Study Visit Day 29. For example, all subjects with Clinical Status in Category 7 or 8 recorded for Study Visit Day 29 performed on or after Day 31 may not count as events by Day 29 unless there is additional corroborating data (e.g., Death or Supplemental Oxygen Case Report Forms).

3.3.3. Mechanical Ventilation-Free Survival at Day 29

Subjects who do not report an ordinal score in Category 8 (Death) or Category 7 (hospitalized on invasive mechanical ventilation or ECMO) at any point following randomization up to and including Day 29 will be

considered to have survived free from mechanical ventilation. The proportion of subjects who survive through Day 29 free from mechanical ventilation will be estimated using a Kaplan-Meier method, allowing definition of time-to-event and time-to-censoring for all subjects.

The time-to mechanical ventilation or death is defined as the elapsed time in days from randomization to the earliest day at which the subject requires mechanical ventilation or dies. The day the subject requires mechanical ventilation is defined as the first day reporting an ordinal score in Category 7. Note (as in Section 3.3.4), this should be the date the subject is assessed, and not the date the score is reported. The time-to-event for subjects discharged to hospice or other end-of-life care prior to Day 29, but for whom a death date is unknown and with Day 60 data unavailable, will be the number of days from randomization to discharge.

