4.2.6. Blinding

As both arms are receiving remdesivir, the remdesivir product is not blinded and study infusions can be labeled accordingly. The baricitinib/placebo component is blinded. Baricitinib and placebo tablets are identical in appearance. The dexamethasone/placebo IV component is blinded. Dexamethasone and intravenous placebo are identical in appearance.

Unblinding of the study will occur after all subjects enrolled have reached the end of study, these visits are monitored, and data is cleaned or if the DSMB recommends unblinding. Data through Day 29 will be locked prior to the completion and lock of Day 60 data. DMID and the SDCC will be unblinded after the Day 29 database lock. Clinical sites will not be unblinded to subject-level treatment assignments until after the Day 60 database lock.

If a subject's clinical status worsens to require mechanical ventilation (ordinal 7), the treating clinician may request unblinding in order to use the prior treatment assignment to inform future treatment. See protocol Appendix D Section 6.3.2.2.

If a Serious Adverse Event occurs, that is thought to be related to the study drug, and the treating clinician believes that knowledge of the treatment arm may change the therapy provided to the patient, the individual subject can be unblinded. If unblinded for SAE, the investigator may decide to have the blinded study product and/or remdesivir infusions discontinued based on the adverse event that led to unblinding and the benefit-risk analysis. See protocol Appendix D Section 6.3.2.3.

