There will also be a sensitivity analysis of the primary, secondary, and mortality outcomes to evaluate the effect of concomitant therapy including experimental treatment and off-label use of marketed medications that are intended as treatment for COVID-19 and are given to patient prior to and during the study. A blinded review of the concomitant medication data will be performed by the medical monitor to identify medications that fall into any of the following categories of “Medications of Interest”:

- Vaccine for SARS-CoV-2 (Pfizer, Moderna, or other) including 1 or 2 doses received
- Antivirals
 - Protease inhibitors
 - Polymerase inhibitors
- Other Potential Treatments for COVID-19
 - Aplidin® (plitidepsin)
 - Colchicine (Colcrys)
 - Monoclonal antibodies targeting the spike protein of SARS-CoV-2 including casirivimab, imdevimab and bamlanivimab
 - Ivermectin (stromectol, Soolantra, Sklice)
- Corticosteroids
- Renin-angiotensin system (RAS) Inhibitors and HMG-CoA reductase inhibitors (statins)
- Other anti-inflammatory drugs
 - Monoclonal Antibodies Targeting Cytokines
 - Other Biologic Therapies

Summaries of subjects who report use of the categories and subcategories of therapies/treatments will be provided. Note that after the blinded review of the medications, additional categories/sub-categories may be defined and/or categories/sub-categories may be combined.

In addition, the sensitivity analyses will consider the following categories (individually):

- Any Medication of Interest
- Vaccines to SARS-CoV-2
- Antivirals
- COVID-19 treatments
- Monoclonal antibody treatments for COVID-19
- Corticosteroids
- RAS Inhibitors and HMG-CoA reductase inhibitors (statins)
- Other Anti-Inflammatory Drugs

Three initiation and duration groups will be constructed for each of the above categories:

1. Prior and During: Subjects taking medication of interest before randomization and during study (on or after Day 1).
2. Prior Only: Subjects taking medications of interest prior to randomization but stopping prior to randomization.
3. During Only: Subjects initiating medications of interest during the study (on or after Day 1).

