For the analysis of mechanical ventilation free survival, subjects will be censored at the time of medication/therapy initiation. For the analysis of the key secondary outcome, if a subject reports use of any of the medications/therapies prior to their Day 15 assessment, then the subject's last clinical status score prior to medication/therapy use will be used as their Day 15 outcome. For the mortality analyses, subjects will be censored at the time of medication/therapy initiation. For the analysis of the proportion of subjects that do not progress to Clinical Status Ordinal Score of 6, 7, or 8 by Day 29, subjects will be censored at the time of medication / therapy initiation. For the recovery analyses, subjects will be censored at the time of medication/therapy initiation. If a subject recovered prior to use of any of the medications/therapies, then the subject will still be counted as a recovery in the sensitivity analysis.

The effect of on-study treatment on select efficacy outcomes will also be explored among subjects who reported use of HMG-CoA reductase inhibitors (statins), angiotensin receptor blockers (ARBs), or angiotensin converting enzyme inhibitors (ACEIs) via subgroup analyses.

Lastly, the effect of treatment on the primary and key secondary efficacy outcomes will be explored via regression modeling controlling for age, duration of symptoms prior to randomization, baseline d-dimer, and baseline CRP values as continuous covariates.

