9.8. Concomitant Medications

Concomitant medications will be coded to the Anatomical Therapeutic Classification using the WHO Drug Dictionary. The use of prior and concomitant medications taken during the study will be recorded on the CRFs. Concomitant medication and corticosteroid use will be presented in subject listings ([Listing 9](#) and [Listing 10](#)). The use of concomitant medications during the study (regardless of whether the medications were started prior to enrollment or after enrollment) will be summarized by ATC1, ATC2 code, actual baseline ordinal score and treatment group for the As Treated population ([Table 55](#)).

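### Section 9.1.2 ends medication collection at about Day 15, but the concomitant-therapy sensitivity analyses censor on medication start out to Day 29; the passages need reconciling and the tables a stated limit

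*SAP*

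**What the plan says.** Section 9.1.2 is the only place in the SAP that gives medication collection an end point. It covers current drugs and "medications taken within 7 days prior to enrollment through approximately Day 15 or early termination (if Day 15), whichever occurs first". The bracketed condition does not parse as written. Section 9.8 is looser: "The use of prior and concomitant medications taken during the study will be recorded on the CRFs", with no end day.

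Section 6.4 sets up a sensitivity analysis covering experimental agents as well as "off-label use of marketed medications that are intended as treatment for COVID-19 and are given to patient prior to and during the study". It groups subjects by when use began; the on-study group is any start on or after Day 1, with no upper limit. The start date then drives the analysis. For the primary endpoint, "For the analysis of mechanical ventilation free survival, subjects will be censored at the time of medication/therapy initiation". For death, "For the mortality analyses, subjects will be censored at the time of medication/therapy initiation". The same rule applies to progression to score 6, 7 or 8 and to recovery.

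The outputs are Table 19 (ventilation-free survival), Table 27 (progression) and Table 32 (recovery), all to Day 29, and Table 73 (death), at both Day 15 and Day 29. Each carries a footnote telling the reader that users were censored when they received the drug.

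**The concern.** An analysis that censors at drug start needs start dates over its whole horizon. Read literally, the SAP stops collecting them about halfway. A subject who begins a corticosteroid on Day 12 is censored on Day 12. One who begins it on Day 17 has no record, stays in the risk set and is treated as unexposed. The table footnotes would then be untrue for the second subject.

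What is at stake is how far a robustness statement can reach. If the Day 29 results with this censoring resemble the main results, a report could say that concomitant therapy does not explain the Day 29 findings, although exposure was recorded for only part of that period. Day 29 mortality matters most here. It is fourth in the fixed testing sequence of Section 6.8, and Table 73 is its check on concomitant therapy. Late treatment choices may also depend on arm: Section 4.2.6 provides that at score 7 "the treating clinician may request unblinding in order to use the prior treatment assignment to inform future treatment", and states no day limit. Missed use therefore cannot simply be assumed to balance between arms.

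**Working it through.** The SAP states no figure for this point, so there is nothing to reproduce. The check compares two time windows and then goes through the outcomes.

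**Inputs**
- End of medication collection: about Day 15 or early termination, whichever is first (Section 9.1.2).
- Horizon of the sensitivity analyses: Day 29 for Tables 19, 27 and 32; Day 15 and Day 29 for Table 73.
- Elapsed time: Day 29 and Day 15 "represent 28 and 14 days post-randomization, respectively" (Section 3.3.2).
- Median days to recovery in ACTT-2 (Section 2): 7 and 8 overall; 5 and 6 on low-flow oxygen; 10 and 18 on high-flow oxygen or non-invasive ventilation. Each pair is combination arm, then control.

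**Uncovered window.** 28 − 14 = 14 days, and 14/28 = 50% of the calendar days to Day 29. This is a share of days. It is not a share of events, of person-time at risk or of drug starts.

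**Does the SAP handle starts after the window?** Sections 6.4 and 6.5 and the programming notes to the four tables contain no truncation at Day 15, no extension of collection and no stated limitation. Table 59, which shows use of these drugs by study day, stops at Day 11.

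**Outcome by outcome, if Section 9.1.2 governs**
- *Day 15 ordinal score and Day 15 mortality:* inside the window, so not affected.
- *Ventilation-free survival and progression (Tables 19 and 27):* a drug started after ventilation cannot matter, because score 7 is already an event for both. The gap concerns only subjects still event-free after about Day 15 who then start a drug.
- *Recovery (Table 32):* Section 6.4 keeps recoveries that precede drug use, so only subjects unrecovered after about Day 15 are exposed.
- *Mortality (Table 73, Day 29 part):* every subject alive after about Day 15 is exposed, including those ventilated earlier.

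**How many might still be unrecovered?** For illustration only, assume exponential recovery, so the share unrecovered after 14 days is 2^(−14/median):
- median 5: 14%; median 6: 20%
- median 7: 25%; median 8: 30%
- median 10: 38%; median 18: 58%

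This indicates who remains at risk for late recovery. It says nothing about how many would start a drug of interest after Day 15. The SAP gives no rate for that, so neither the number misclassified nor the bias can be calculated.

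**The case against.** The strongest reply is that the window is not settled. Section 9.8 refers to use during the study with no Day 15 stop. The notes to Listings 9 to 11 provide for drugs ongoing at end of study. The notes to Tables 57 and 58 set only a lower date limit. The sentence in Section 9.1.2 is garbled, and collection is ultimately a matter for the protocol and case report form, which are not at hand. This stands in part. None of these passages extends collection of new starts to Day 29, but together they mean the gap cannot be asserted as fact. It is conditional on Section 9.1.2.

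The second reply is that little depends on these tables. Section 8.2 calls such analyses supportive, they sit outside the testing hierarchy of Section 6.8, and their treatment comparisons carry no p-values. This stands in full: the primary test, the type I error control and the key secondary endpoint are untouched.

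A reader might infer that crossover after unblinding at score 7 compromises all four outcomes. The documents do not support that. Score 7 is already the event for ventilation-free survival and progression, so that route leaves only Day 29 mortality and late recovery. Nor are these purely crossover analyses, since the medications of interest also include vaccines, antivirals, statins and renin-angiotensin inhibitors. And although the blinded courses are capped at 10 and 14 doses, the SAP does not say that open-label treatment follows.

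**Conclusion.** The point holds in a limited form. Sections 9.1.2 and 9.8 do not agree on how long medications are recorded, and Section 6.4 relies on start dates out to Day 29. If Section 9.1.2 governs, starts after about Day 15 are not captured and those subjects count as non-users for the remainder of follow-up.

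Its reach is supportive sensitivity analyses only, mainly the Day 29 part of Table 73 and, in Table 32, subjects unrecovered at Day 15. Tables 19 and 27 are touched only through subjects still event-free at that time. Reading the 50% of uncovered calendar days as half the exposure or half the information would go too far, because many subjects may already have recovered by Day 15. The size and direction of any bias cannot be determined from the SAP.

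The conclusion rests on the stated window being the operative one, with no other source of later start dates feeding these tables.

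**What to change.** 1. Reconcile Section 9.1.2 with Section 9.8, state one end day for medication collection, and repair the bracketed early-termination condition in Section 9.1.2. If collection in fact runs to Day 29, correcting Section 9.1.2 is all that is needed.
2. If collection ends at about Day 15, add to Tables 19, 27 and 32 a version in which all subjects are administratively censored at Day 15. Table 73 already reports Day 15.
3. Keep the Day 29 versions, but say in Section 6.4 that the Day 15 versions are the ones that support any statement about concomitant therapy.
4. Footnote the Day 29 results in all four tables: starts after about Day 15 are not captured, and those subjects remain in the analysis as non-users.

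The cost is SAP wording, one added cut-off in three tables and a footnote in four, with no new data. The downside is that the trial makes no statement about robustness to concomitant therapy for Days 16 to 29. If Section 9.1.2 governs, the recorded data could not support one anyway.

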9.2. Measurements of Treatment Compliance

Section [7](#) provides the descriptions of summaries of key treatment compliance milestones/variables. Individual subject listings will be presented for all subjects who discontinued dosing ([Listing 2](#)). Individual subject listings will be presented for all subjects who missed, halted or slowed any dose ([Listing 12](#)).

9.3. Adverse Events

For the calculation of incidence of adverse events (i.e., on a per subject basis), each subject will only be counted once and any repetitions of adverse events within a subject will be ignored; the denominator will be the number of subjects in the As Treated population. All adverse events reported and treatment emergent will be reported in tables and listings; treatment emergent events are adverse events or events increasing in severity anytime following the initiation of administration with any study product (baricitinib, dexamethasone, remdesivir, or any placebo).

An overall summary by treatment arm and actual baseline ordinal score of adverse events is presented that includes, but not limited to: subjects with at least one event, at least one related event, at least one SAE, at least one related SAE and at least one AE leading to early termination for all subjects ([Table 60](#) and [Table 61](#)).

Adverse events occurring in 5% of subjects (by MedDRA preferred term) in any treatment group will be presented ([Table 63](#)).

The proportion of subjects reporting at least one adverse event will be summarized by MedDRA system organ class and preferred term for each treatment arm, actual baseline ordinal score and overall. Denominators for percentages are the number of subjects in the Treated population.

The following summaries for adverse events will be presented by MedDRA system organ class, preferred term, baseline ordinal score and treatment group:

- Renal adverse events by preferred term ([Table 64](#));
- Hepatic adverse events by preferred term ([Table 65](#))
- Related adverse events by MedDRA system organ class and preferred term ([Table 66](#));
- Subject listing of non-serious adverse events ([Listing 13](#)) and listing of related adverse events ([Listing 14](#));
- Bar chart of non-serious related adverse events by actual baseline ordinal score and MedDRA system organ class ([Figure 25](#), [Figure 26](#));

A table of new diagnoses between the Day 29 visit and the Day 60 visit will be summarized by condition, treatment arm, actual baseline ordinal score and overall ([Table 67](#)). Conditions reported at the Day 60 visit will be listed ([Listing 30](#)).

9.4. Deaths, Serious Adverse Events and other Significant Adverse Events

Serious adverse events will be summarized by MedDRA system organ class and preferred term ([Table 62](#)). Listings of death and other serious adverse events will be presented, including Subject ID, treatment group, Adverse Event Description, Number of Days Post Dose (Duration), Number of Days Post Dose the Event Became Serious, Reason Reported as an SAE, Severity, Relationship to Treatment, Alternate Etiology if not Related, Action Taken with Study Treatment, Subject Discontinuation, Outcome, MedDRA SOC, and MedDRA PT ([Listing 15](#) and [Listing 17](#)).

The number of subjects who die by Day 15 and Day 29 will be presented by treatment arm. The 14-, 28-and exploratory 60- day mortality rate, which will use Kaplan-Meier estimator, will be presented ([Table 69](#)). Differences in time-to-event endpoints by treatment will be summarized with Kaplan-Meier curves ([Figure 28](#), [Figure 29](#), [Figure 30](#)).

Mortality through Day 15 and 29 will also be analyzed as a time to event endpoint (see Section 3.3). A table will present median time to event along with 95% confidence intervals overall for each treatment arm along with the hazard ratio estimate and log rank p-values (Table 70). Differences in time-to-event endpoints by treatment will be summarized with Kaplan-Meier curves (Figure 27). Analyses of mortality will be performed in the mITT and the As Treated analysis populations (Table 71). As a supplemental analysis, a Cox model will be fit with binary indicators for treatment group and actual baseline ordinal score as well as a treatment * actual baseline ordinal score interaction term (Table 74). The model will be fit in the mITT and As Treated analysis populations. The treatment group hazard ratios and CIs and the interaction term p-value will be reported. Finally, the results of the subgroup and sensitivity time-to event analyses described in Section 6.4 will be presented in a table (Table 72 and Table 73). A restricted mean survival time analysis of mortality will be performed as an exploratory analysis. The restricted mean mortality time estimates will be provided for each treatment group and randomized actual baseline ordinal score stratum as well as the difference in restricted mean recovery time between treatment groups within each of the actual baseline ordinal score strata (Table 75).

Rates of Grade 3 and 4 AE occurrence will be summarized by treatment arm (Table 76). Rates of SAE occurrence will also be compared between treatment arms using Barnard's exact test and presented. Further, the composite endpoint of the occurrence of death, SAE, or Grade 3 or 4 AE described in Section 3.3 will be analyzed as a time to event outcome. A table will present median time to event along with 95% confidence intervals overall for each treatment arm along with the hazard ratio estimate and log rank p-values (Table 77). Differences in time-to-event endpoints by treatment will be summarized with Kaplan-Meier curves (Figure 33).

A summary of the infection culture results will be summarized by treatment group and AE severity (Table 78). The anatomical location(s) of the infection and causative pathogen(s) determined by culture will be summarized (Table 79, Table 81, Table 83). A listing of culture results will be generated (Listing 16). Infections considered to be opportunistic, as identified by the sponsor, will also be included in the summaries (Table 80, Table 82, Table 84). Both summaries will be repeated by Dexamethasone use prior to enrollment (Table 85 and Table 86).

A summary of venous thromboembolisms, comprised of deep vein thrombosis and pulmonary embolisms by Treatment Group, will be included (Table 87).

